## 8.7 Secondary endpoints

The ICIQ-SF is used as a validated questionnaire [36] to assess the severity and impact of incontinence by the patient in several studies [30] [37].

An improvement of 2.5 score points is specified as the MID in Nystrom et al [38]. In the study by Sjöström [33] an improvement of 20% is aimed for, in the study by Asklund [8] an improvement of 2.9 points (based on the results of the Sjöström study) is described as the target (3.2 points were achieved in the study). Based on the various data in the

Kranus Health GmbH\_DINKS

literature, we are aiming for an improvement of 2.9 points in the ICIQ-SF in this study (see **Table 3:** ICIQ-SF).

**Table 3:** ICIQ-SF

Tool/ Parameter	Questionnaire	Possible answers	Result range	Targeted improvement
ICIQ-SF	3	1. Question: 0-5 2. Question: 0,2,4,6 3. Question: 0-10	0-21	≥ 2.9 points

As further secondary endpoints, the disease-related quality of life is measured using the validated I-QOL and the patients' level of activation in relation to their healthcare using the PAM-13 questionnaire, which has also been validated. The change in specific incontinence episodes, measured using the S/U-IQ questionnaire, is also recorded. Other endpoints include changes in micturition frequency during the day and night, reduction in pad use, decrease in imperative urge to urinate and an increase in functional bladder capacity as well as surveys on body weight changes, treatment failure and overall improvement (PGI questionnaire) and app use in the intervention group.

### 8.8 Statistical analysis

In general, continuous data is summarised using descriptive statistics, i.e. with the number of observations, mean, standard deviation, minimum, median and maximum. For some variables such as the primary endpoints, the change from baseline to the end of the study (change from baseline, CfB) is also output and summarised as "post-baseline". Where appropriate, 95% confidence intervals are also calculated and reported.

Categorical data is summarised using absolute and relative frequency.

The hypotheses for analysing the mean group differences in the primary endpoint are:

$$H_0: \text{rel-CfB arm A} = \text{rel-CfB arm B}$$

versus

$$H_1: \text{rel-CfB Arm A} \neq \text{rel-CfB Arm B}$$

This is analysed using an analysis of covariance with the factor treatment group and the covariate baseline. As a sensitivity analysis, the relevant changes are analysed using 2-sample Wilcoxon tests.

The continuous target variables are analysed analogously with the CfBs. The results of these analyses are presented graphically using progression curves (mean values and LS mean changes) of the original mean values and the CfBs. Ordinal endpoints (e.g. PGI) are compared between the groups using 2-sample Wilcoxon tests.

Binary endpoints (rates) are compared using Fisher tests; in addition, 95% CIs are provided for comparison between groups.

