## 6.8 Pre-screening, medical history, inclusion procedure

In the first step, the prospective patient registers via the study portal and fills out a few questions to initially check potential eligibility based on the inclusion and exclusion criteria. If the result of the check is positive, the patient registers in Evident IQ's Dacima study tool, receives a patient ID, fills out a medical history form and provides proof of diagnosis. If the criteria are met, an appointment is made with the study centre, which checks the inclusion and exclusion criteria again. The patient is then informed about the study and can ask questions about the study and its procedure. Once the consent form has signed voluntarily and independently, the patient is included in the study.

Essential basic information (study centre, date of consent, year of birth, age, gender, inclusion/exclusion criteria, etc.) is stored in the eCRF. All patients record their incontinence episodes over a period of three days (3 x 24 h). The baseline data collection then takes place in the study tool, followed by randomisation to the respective study arm in the study tool. For documentation purposes, a form on the randomisation result (block randomisation 1:1) is generated via the study tool. Furthermore, the intervention patients fill out a micturition diary in the app to record micturition frequency, drinking volume and other symptoms.

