## Kranus Health GmbH\_DINKS

Multiplicity: The primary endpoint (1) and the first 3 secondary endpoints (2) - (4) are tested sequentially according to the method of a priori ordered hypotheses: The primary endpoint (1) relative change rel-CfB-IEF week 12 with respect to baseline of incontinence episodes is analysed using an analysis of covariance with the factor treatment group and the baseline value of the IEF as covariate; the significance level is 5% 2-sided. If significance is reached for endpoint (1), endpoint 2 (change in the ICIQ-SF questionnaire) is tested analogue to the 5% 2-sided level. If significance is reached for endpoint (2), endpoint (3) (change in quality of life in the I-QOL questionnaire) is tested 2-sided analogue to the 5% level. If significance is reached for endpoint 3, endpoint 4 (PAM-13) is tested 2-sided analogue to the 5% level. The other endpoints are analysed descriptively with p-values and 95% CIs. The FAS (ITT) is the primary evaluation collective for efficacy; missing values for the main outcome variables (1) - (4) are imputed using the JtR method.

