## Subgroup analyses:

Descriptive subgroup analyses are performed for the primary and secondary efficacy variables using the ICD code:

- N39.3 Stress incontinence [stress incontinence]
- N39.42 Urge incontinence
- Mixed incontinence - both codes

and using the S/U-IQ (Stress/Urge Incontinence Questionnaire and Classification System) for the indications:

- pure stress urinary incontinence ( $SUI \geq 4$ ,  $UUI=0$ ),
- Mixed urinary incontinence, predominantly stress component ( $SUI > 0$ ,  $SUI > UUI$ ;  $UUI > 0$ ),
- balanced mixed urinary incontinence ( $SUI > 0$ ,  $SUI=UUI$ ),
- Mixed urinary incontinence, predominantly urge component ( $SUI > 0$ ,  $UUI > 0$ ,  $UUI > SUI$ )
- Pure urge incontinence ( $UUI \geq 4$ ,  $SUI =0$ )

carried out.

Further subgroup analyses are carried out:

- Medication for the treatment of incontinence (yes/no),
- Premenopausal/menopausal/postmenopausal status,
- Age categories < 45, 45-60, > 60 years,
- BMI,
- Country of birth,
- Level of education,
- Secondary diseases,
- Smoking behaviour,
- Alcohol consumption,
- Number of births,

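### Adding ICD incontinence type to the ANCOVAs for endpoints (1)–(4), with an interaction estimate for the type subgroups, would be a nearly free improvement to a valid analysis

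*Combined protocol and SAP*

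**What the plan says.** The confirmatory models contain treatment and the baseline value, and nothing else. After stating the primary hypotheses, section 8.8 says: "This is analysed using an analysis of covariance with the factor treatment group and the covariate baseline". For the primary endpoint, the multiplicity paragraph of section 8.8 specifies an "analysis of covariance with the factor treatment group and the baseline value of the IEF as covariate". For the other continuous endpoints, section 8.8 says "The continuous target variables are analysed analogously with the CfBs". The statistical methods entry of the synopsis (1.4) agrees.

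Section 6.8 describes allocation only as "block randomisation 1:1" and names no strata. It also fixes the order of events. At registration the woman "fills out a medical history form and provides proof of diagnosis". Later, "The baseline data collection then takes place in the study tool, followed by randomisation to the respective study arm in the study tool". Type is therefore a pre-randomisation variable, and because it is an inclusion criterion (3.1) every woman has one.

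In the analysis, type appears only under the subgroups: "Descriptive subgroup analyses are performed for the primary and secondary efficacy variables using the ICD code", followed by a second split by S/U-IQ class. Forest plots are planned. No treatment-by-type interaction estimate is mentioned.

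**The concern.** The trial pools three conditions that sections 4.1.1 to 4.1.3 separate by mechanism. If type predicts the week-12 value beyond what baseline predicts, leaving it out of the model has two costs. Residual variance is larger than it need be, and a chance difference in type mix between the arms is not corrected. The first matters most for I-QOL, which sets the sample size at 80% power, and then for PAM-13, which is tested only if I-QOL succeeds.

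The second matter is how the subgroup results will be read. Separate estimates per type, in groups of very different size, can look as if the app works in one type and not in another when the true effect is the same. An interaction estimate answers that question directly.

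**Working it through.** **Inputs from the documents.** Two-sided 5% level. Standardised effects from 8.4: IEF 0.7, ICIQ-SF 2.9/3.2 ≈ 0.9, I-QOL 6.3/14 = 0.45, PAM-13 6/12 = 0.5. I-QOL total from the synopsis: 158 + 40 = 198, so 79 evaluable per arm. Type shares from 4.2: stress 50%, urge 14%, mixed 32%.

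**Input not in the documents.** The partial R² of type given baseline, taken as 0 to 0.15.

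**Reproducing the plan's figure.** For I-QOL at 0.45 and 80% power, the two-sample t calculation gives 79 per arm, or 158. Then 158/0.8 = 197.5, rounded up to 198. The synopsis figure reproduces. Section 8.4 gives 2 × 90 for the same inputs. That number has 85.1% power, not 80%, so the two sections must be reconciled. The figures below use 79.

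**Power with type added.** Non-centrality = (d/s)/√(1 − R²) × √(n/2), with degrees of freedom 2n − 2 unadjusted and 2n − 4 with type. For I-QOL unadjusted: 0.45 × √39.5 = 2.83, power 80.3%. At R² = 0.10: 2.83/0.949 = 2.98, power 84.2%.

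| Endpoint, 79 per arm | Type omitted | R² = 0 | 0.02 | 0.05 | 0.10 | 0.15 |
|---|---|---|---|---|---|---|
| I-QOL | 80.3% | 80.2% | 81.0% | 82.2% | 84.2% | 86.2% |
| PAM-13 | 87.8% | 87.8% | 88.4% | 89.3% | 90.9% | 92.3% |
| IEF (primary) | 99.2% | 99.2% | 99.3% | 99.4% | 99.6% | 99.7% |
| ICIQ-SF | >99.9% | >99.9% | >99.9% | >99.9% | >99.9% | >99.9% |

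The table charges only the two degrees of freedom. Because type and arm are not exactly balanced, the treatment contrast also loses roughly 2/154 ≈ 1.3% in variance on average (2/194 ≈ 1.0% with all 198 women). The break-even partial R² is therefore about 0.01. For I-QOL, 0.02 of R² is worth about 0.8 point (80.2% to 81.0%), so this extra charge would take about half a point off each adjusted I-QOL entry.

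**Chance imbalance.** Rescaling the 4.2 shares to 100% gives a stress share of 50/96 = 52%. With 99 per arm, the stress shares of the arms differ by 10 percentage points or more with probability 17.6%, and by 15 or more with probability 3.9%. If stress and the other types differed by an assumed 0.3 SD given baseline, a 10-point imbalance shifts the contrast by 0.10 × 0.3 = 0.03 SD. The standard error is √(2/99) = 0.142 SD, so the shift is about 0.2 standard errors. Type I error given that imbalance would be 5.5%. Averaged over randomisations it is 5%.

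**Per-type comparisons.** Of 79 evaluable per arm, 79 × 50/96 ≈ 41 have stress and 79 × 14/96 ≈ 11.5 have urge incontinence. Suppose the effect is identical in every type at the planned IEF value of 0.7. The stress comparison then has about 88% power, and the urge comparison 35% (11 per arm) to 37% (12 per arm). The chance that stress is significant and urge is not is about 0.88 × (1 − 0.36) = 0.56, with no true difference between types.

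**Precision of the interaction.** The stress-minus-urge contrast has standard error √(2/41 + 2/11.5) = 0.47 SD, so its 95% interval is about ±0.92 SD. That is wider than the planned effect itself.

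**The case against.** The strongest reply is that nothing here is wrong. Treatment plus baseline is prespecified, stated consistently in the synopsis and in 8.8, and valid under unstratified allocation. Since type is not a stratification factor, no design feature obliges the model to include it. All of this stands. A reader might infer that omitting type biases the comparison or inflates the error rate. The documents do not support that, because allocation is random and the ordinary confidence interval already allows for chance imbalance.

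The precision gain is assumed. Sections 4.4 and 4.4.3 report that conservative measures work in all three types. That concerns the treatment effect rather than prognosis, but no section shows that type is prognostic given baseline. It is tempting to say that adjustment can only help. Below a partial R² of about 0.01 it does not. The 80.3% is also a t-test figure on change scores with s = 14. The planned ANCOVA already uses baseline, so its power may be higher.

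On subgroups, the plan labels the analyses descriptive and makes no per-type claim, and the interaction will be imprecise. Both are true. The imprecision is what a reader of the forest plot needs to see, and the interval shows it.

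Missing stratification can hardly be remedied now. Recruitment was scheduled to end on 31.10.2024 and version 2.1 is dated 14.11.2024. Adjustment in the model remains available, because 8.12 says a detailed SAP is still to be written.

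**Conclusion.** This is a low-cost improvement to a valid plan. The facts hold: type is known before randomisation, is not a described stratum, is absent from the four ANCOVAs and leads the subgroup list without an interaction estimate. The size is modest and conditional. For an assumed partial R² of 0.02 to 0.10, I-QOL gains roughly 1 to 4 power points and PAM-13 roughly 1 to 3. If type is not prognostic, the loss is under 0.1 point from degrees of freedom, or about half a point for I-QOL when chance non-orthogonality is counted too.

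A reader might conclude that the primary result is at risk. It is not: on the plan's own inputs the primary endpoint has 99.2% power at 79 per arm and ICIQ-SF more than 99.9%, and neither changes materially.

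The case for the interaction estimate does not depend on type being prognostic. It rests on unequal subgroup sizes, using the literature shares in 4.2 as a stand-in for the trial's own mix.

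**What to change.** Before evaluation, change 8.8, the matching synopsis entry and the SAP as follows.

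1. For endpoints (1) to (4), specify an ANCOVA with factors treatment group and ICD incontinence type (N39.3 only, N39.42 only, both codes) and the baseline value as covariate.
2. Name the same type factor in the JtR imputation model, whose variables are not listed at present, so that imputation and analysis models agree.
3. Use ICD type rather than S/U-IQ class. The classification in A1.5 leaves some patterns in no class, for example 1 to 3 stress episodes per week with no urge episodes, or the reverse.
4. For the descriptive analysis by type, take the forest-plot estimates from a separate model with a treatment-by-type interaction. Report the interaction estimate with its confidence interval, and state that it will be imprecise for urge incontinence.
5. Reconcile the I-QOL sample size between the synopsis (158) and 8.4 (2 × 90).

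The cost is wording in the protocol and SAP, two degrees of freedom in each confirmatory model, and a negligible loss of power if type turns out not to be prognostic. No new data are needed.

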### 8.2 Primary endpoint

- 1) Relative change (rel-CfB-IEF) of the IEF from baseline to week 12 in relation to baseline

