### 8.3 Secondary endpoints

- 2) Change in ICIQ-SF from baseline to week 12
- 3) Change in I-QOL from baseline to week 12
- 4) Change in the PAM-13 questionnaire from baseline to week 12
- 5) PGI-I questionnaire (overall improvement after treatment) at the end of the study
- 6) Proportion of patients without incontinence (cured patients) at the end of the study
- 7) Reduction in micturition frequency during the day
- 8) Reduction in micturition frequency at night
- 9) Reduction in pad consumption
- 10) Reduction of the imperative urge to urinate
- 11) Change in functional bladder capacity
- 12) Reduction in body weight
- 13) Reduction in the proportion of patients with treatment failure within the study period
- 14) Proportion of patients with at least 50% reduction in IEF from baseline to week 12
- 15) Reduction in the frequency of stress incontinence episodes in the S/U-IQ
- 16) Reduction in the frequency of urge incontinence episodes in the S/U-IQ

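### For the descriptive binary endpoints (6), (13) and (14), Fisher's test beside a 95% CI of unnamed method costs some power and can contradict that CI; one baseline-adjusted model would serve better (minor)

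*Combined protocol and SAP*

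**What the plan says.** Section 8.8 sets the method by type of endpoint.

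- Primary endpoint: "This is analysed using an analysis of covariance with the factor treatment group and the covariate baseline". The continuous secondary endpoints are handled in the same way.
- Binary endpoints: "Binary endpoints (rates) are compared using Fisher tests; in addition, 95% CIs are provided for comparison between groups". In section 8.3 these are (6), "Proportion of patients without incontinence (cured patients) at the end of the study"; (13), "Reduction in the proportion of patients with treatment failure within the study period"; and (14), the share of women whose IEF falls by at least half from baseline.
- Ordinal endpoints: "Ordinal endpoints (e.g. PGI) are compared between the groups using 2-sample Wilcoxon tests".
- Check on the primary: "As a sensitivity analysis, the relevant changes are analysed using 2-sample Wilcoxon tests".

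Only endpoints (1) to (4) are in the ordered test sequence. The multiplicity paragraph of 8.8 makes all the others descriptive, but they still carry p-values and 95% CIs. Section 6.8 has every woman complete a three-day incontinence record before randomisation, so baseline IEF is available for all. Section 8.12 announces a detailed SAP before the evaluation.

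**The concern.** The plan adjusts every continuous endpoint for baseline and gives no reason for treating the binary ones differently. Three costs could follow.

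1. Fisher's test is conservative at this sample size, so real differences in cure or response are detected less often.
2. The p-value comes from one method and the CI from another, unnamed one. A report could show p > 0.05 next to an interval that excludes zero.
3. A covariate already collected, and likely to predict at least (6), goes unused.

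Cure, treatment failure and 50% response are listed objectives in the synopsis. Section 8.6 calls a 50% reduction clinically relevant, so (14) is the natural responder reading of the primary. Readers will look at these results even though they are descriptive.

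**Working it through.** **Inputs.** 99 per arm (section 6.1), two-sided 5% (8.8). The documents give no event rate, power or sample size for (6), (13) or (14), so all rates below are assumptions.

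**The plan's own figure.** The only related figure is the primary's 2 × 44 in section 8.4. With d/s = 0.7 and 90% power, n = 2(1.960 + 1.282)²/0.7² = 42.9, so 43 per arm by the normal approximation and 44 by the t-test. It reproduces, but it does not concern the binary endpoints.

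**Step 1: size and power.** Enumerate every pair of event counts (i, j) with 0 ≤ i, j ≤ n, weight each by its two binomial probabilities, and add the weights where p ≤ 0.05. The comparator is the pooled z test, z = |i − j|/n ÷ √(2m(1 − m)/n), with m = (i + j)/2n.

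True size of Fisher at 99 per arm: 2.1%, 2.8%, 3.3% and 3.5% at common rates of 5%, 10%, 20% and 30%. The z test lies between 4.3% and 5.2%.

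| Assumed rates | Fisher, 99/arm | z test, 99/arm | Fisher, 79/arm | z test, 79/arm |
|---|---|---|---|---|
| 15% v 5% | 58.0% | 67.8% | 47.4% | 57.7% |
| 25% v 10% | 75.7% | 81.1% | 64.1% | 72.2% |
| 50% v 30% | 78.6% | 82.6% | 67.6% | 73.0% |
| 60% v 30% | 98.8% | 99.2% | | |
| 40% v 10% | 99.9% | 99.9% | | |

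The 79 is half of the 158 in the synopsis I-QOL calculation, about what 20% dropout would leave (0.8 × 99 = 79.2).

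**Step 2: p-value against CI.** Take 20 v 10 events among 99 each. Fisher gives p = 0.073. The Wilson limits are 0.1348 to 0.2915 for 20/99 and 0.0558 to 0.1760 for 10/99. The Newcombe limits for the difference of 0.1010 are:

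- lower: 0.1010 − √[(0.2020 − 0.1348)² + (0.1760 − 0.1010)²] = 0.0003
- upper: 0.1010 + √[(0.2915 − 0.2020)² + (0.1010 − 0.0558)²] = 0.201

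The interval excludes zero while p exceeds 0.05. With 14 v 5 events, p = 0.051 and the CI is 0.008 to 0.178. At true rates of 15% v 5% this conflict arises in about 7% of trials with Newcombe intervals and 10% with Wald intervals.

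**Step 3: what baseline adds.** Three-day counts were simulated with a baseline of at least 1 per day, in three assumed scenarios (1,000 trials each, Monte Carlo error about 1 to 1.5 points). The middle column below is the enumeration of step 1 at the simulated average rates.

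| Endpoint, rates | Fisher | Unadjusted z | Logistic, log baseline |
|---|---|---|---|
| (6) 17.2% v 10.8% | 20.8% | 25.6% | 28.4% |
| (6) 10.7% v 6.9% | 9.9% | 15.9% | 16.6% |
| (6) 6.6% v 4.2% | 5.5% | 10.4% | 10.6% |
| (14) 66.6% v 52.0% | 49.7% | 55.8% | 55.3% |
| (14) 58.8% v 45.4% | 42.4% | 48.8% | 47.3% |
| (14) 51.0% v 38.2% | 39.4% | 45.4% | 44.5% |

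Log baseline correlates with (6) at about −0.21 to −0.23 and with (14) at only 0.06 to 0.07. Adjustment adds roughly 0 to 3 points for (6) and nothing for (14). There, the gain of about 5 points comes from dropping Fisher.

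The gain depends on how prognostic baseline is. At 45% v 25%, the adjusted model has 83%, 85%, 90% and 94% power for a log-odds ratio per SD of baseline of 0, 0.5, 1.0 and 1.5, against 84.5% for the unadjusted test and 80.8% for Fisher.

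**The case against.** The strongest reply is that nothing confirmatory is touched. Endpoints (5), (6), (13) and (14) are outside the ordered sequence and no sample-size calculation covers them. Fisher is conservative but valid, so it creates no false-positive risk. The rates are assumed, the loss vanishes for large effects, and a well-chosen exact interval would limit the p/CI conflict. The announced SAP could settle the details. All of this stands, and it sets the weight. It does not remove the point, because 8.8 still promises p-values and CIs for these endpoints and names no CI method.

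A reader might infer more than the documents support.

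- **That baseline is ignored throughout.** Endpoint (14) is defined against each woman's own baseline, and the primary variable is "Relative change (rel-CfB-IEF) of the IEF from baseline to week 12 in relation to baseline". Scaling by baseline is not the same as adjusting for it, but baseline is not ignored.
- **That the Wilcoxon check on the primary loses power.** On the simulated skewed relative changes it did better than ANCOVA (69%, 61% and 58% against 55%, 57% and 53%). It lost only under assumed normal data (d = 0.45) with a baseline correlation of 0.3 or more: about 87% against 92% at 0.3 and 95% at 0.5. It does drop the covariate and the normality assumption together, so a disagreement with ANCOVA could not be traced to either one. But 8.8 does not say that the check is meant to isolate non-normality, and a simple distribution-free test beside an adjusted main analysis is conventional.
- **That PGI-I loses power.** No calculation shows this, and nothing in the documents shows how strongly baseline IEF predicts PGI-I or (13).

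**Conclusion.** The point holds as a minor improvement to the analysis of (6), (13) and (14). At 99 per arm Fisher's true size is about 2.1% to 3.5% at common rates of 5% to 30%. It gives up about 4 to 10 points of power at moderate assumed effects and almost nothing at large ones. The p/CI conflict is demonstrable under a standard interval, but it is a possibility, not a certainty, because the plan leaves the interval open. Most of the power gain comes from leaving Fisher. Baseline adjustment should help mainly for (6), by an amount that rests on an unknown prognostic strength, and it protects against chance imbalance. The case for change is as much coherence as power. No confirmatory conclusion, alpha or sample size changes.

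**What to change.** In section 8.8, or in the announced SAP before the evaluation, replace the Fisher sentence with wording such as:

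*Endpoints (6), (13) and (14) are analysed by logistic regression with treatment and log baseline IEF. The standardised risk difference, its 95% CI and its p-value are reported from this model. If either arm has fewer than 5 events, Fisher's test is used instead, with a named exact CI.*

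The inclusion criterion of at least one episode per day should keep the logarithm defined. State a rule in case a three-day record shows none.

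Optionally, analyse PGI-I by a proportional-odds model adjusted for baseline IEF; its gain is not quantified here. Keep the Wilcoxon sensitivity test of the primary. A rank ANCOVA with baseline IEF may be added beside it.

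The cost is a few lines of text and code, slightly more analysis work, and loss of exactness when events are sparse, which the Fisher fallback covers. No extra data are needed.
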